## 8 Data Handling Conventions

### 8.1 Missing Data

Missing data occurs when any requested data is not provided, leading to blank fields on the collection instrument. These data will be indicated using a “blank” in subject listing displays. Answers such as “Not applicable” and “Not evaluable” are not considered to be missing data and should be displayed as such.

The details of handling missing data are presented in the corresponding SAP sections (e.g., primary and secondary efficacy analyses, safety analyses).

### 8.2 General Derived Variables

The following sections provide a general description of the derived variables for data analyses.

#### 8.2.1 Reference Dates and Study Day

Reference dates are used to assign study periods relative to IP.

- The reference date for safety, CCI and PK is the start date (and time) of treatment (i.e., the date [and time] of the administration of IP) and will be used to calculate the study day and to assess the baseline value to calculate changes from baseline or shifts to baseline.
- The reference date for efficacy is the date (and time) of randomization and will be used to calculate the time interval for the efficacy time-to-event endpoints and to assess the baseline value to calculate changes from baseline or shifts to baseline.

If the date of interest occurs on or after the reference date, then the study day will be calculated as (date of interest - reference date) + 1. If the date of interest occurs before the reference date, then the study day will be calculated as (date of interest - reference date). There is no study day 0.

### 8.2.2 Durations and Time to Event Data

Durations (e.g., the duration of an AE) calculated in full days (if time is not available) or in partial days (if time is available) are defined as

- event end date - event start date + 1, if time is not available;
- event end date and time - event start date and time, if both end time and start time are available. In this case, the duration needs to be transformed to days.

Thus, there will be no duration of 0 if the time is not available. If an event has missing or partially missing start or end date no duration will be calculated. For durations which usually last less than a day (e.g., the duration of an infusion), the duration will only be calculated if start and end time are available.

For elapsed time (e.g., the time to event), use

- event date - reference date, if time is not available;
- event date and time - reference date and time, if both event and reference time are available. This will require transformation to the desired unit (e.g., days).

Thus, an event which happens on the same date as the reference date will have an elapsed time of 0, if event time or reference time are not available. For the analysis of time-to-event observations that are equal to 0, these values will be set to a very small value (0.0000001) to avoid that the observation is excluded from the analysis in some SAS procedures.

To transform durations or elapsed time which are calculated in days into weeks, divide the number of days by 7; to report in months divide the number of days by 30.4375; to report in

years divide the number of days by 365.25. These algorithms return decimal numbers and ignore the actual numbers of days in the months or years between start date and stop date (i.e., the calendar days are ignored). The "year" used in these algorithms is 365.25 days long, and the "month" is one twelfth of that year.

### **8.2.3 Baseline Definition**

For efficacy endpoints, baseline is defined as the most recent, non-missing value before randomization (including unscheduled visits) unless otherwise stated. If no value before randomization exists, the most recent, non-missing value before IP administration will be used as baseline value.

For safety, baseline is defined as the most recent, non-missing value before IP administration (including unscheduled visits) unless otherwise stated.

### **8.2.4 Change from Baseline**

Change from baseline is calculated as:

- visit value - baseline value.

Percentage change from baseline is calculated as:

- $(\text{change from baseline} / \text{baseline value}) * 100$ .

If either the baseline or visit value is missing, the change from baseline and percentage change from baseline will also be missing.

### **8.2.5 Multiple Assessments**

All data will be reported according to the nominal visit date for which it was assessed (i.e., no visit windows will be applied during dataset creation and the visit will not be re-allocated if the actual visit date deviates from the planned date according to the visit schedule in the protocol). Unscheduled data will not be included in by-visit summaries, but may contribute to the Baseline value, the End of Study (EOS) value, or best/worst case value (e.g., shift tables) and will be displayed in the listings.

If multiple assessments on the same day or on different days are reported for the same scheduled visit, then the assessment for that scheduled visit will be analyzed according to the following rules:

- if an assessment was repeated as safety follow-up (e.g., laboratory value out of normal range) use the initial, abnormal assessment for that scheduled visit;

- in all other cases, use the last valid assessment for that scheduled visit; rationale: the assessment was repeated either because the initial assessment was missing or invalid (e.g., due to technical issues, loss of sample, clotting of sample or other reasons of this type) or the assessment was repeated but the reasons were not collected or unknown.

Data from all assessments (scheduled and unscheduled), including multiple assessments, will be included in the listings.

### **8.2.6 Actual Treatment**

The subject's actual treatment will be derived from the exposure data (kit number from drug administration). If a subject receives a study treatment different from the randomized treatment, the actual treatment is the treatment received.

### **8.2.7 Derived Variables**

The derived variables used for the analysis will be defined and specified in detail in the respective section of the SAP.

#### **8.2.7.1 Subgroup: Sex**

- Male;
- Female.

#### **8.2.7.2 Subgroup: Age Group**

- < 65 years;
- ≥ 65 years of age.

For the demography table, additional categories for subjects < 65 years of age will be displayed:

- < 18 to 29 years;
- 30 to 39 years;
- 40 to 49 years;
- 50 to 64 years.

These categories will not be used in the subgroup analyses for efficacy.

#### **8.2.7.3 Subgroup: Comorbidity**

- Any comorbidity factor present: yes (including hypertension; diabetes; obesity, defined as body mass index [BMI] ≥ 30);

- Any comorbidity factor present: no.

For assignment of comorbidity see Section 9.3.

#### **8.2.7.4 Subgroup: Use of Approved / Emergency-authorization Usage of Anti-COVID-19 Drugs**

- Any concomitant usage of anti-COVID-19 drugs during the trial: yes;
- Any concomitant usage of anti-COVID-19 drugs during the trial: no.

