6.1 Eligibility Criteria

The study population will be selected on the basis of the inclusion and exclusion criteria described in the sections below. Subject eligibility should be reviewed and documented by an appropriately medically qualified member of the investigator's study team before subjects are included in the study. Eligibility may be assessed at the time of hospital admission provided that the subject is randomized within 24 hours.

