#### 9.4 Prior/Concomitant Medications and Procedures

Prior/concomitant medications will be coded using the World Health Organization Drug Dictionary. The version will be provided in the output tables and listings.

The reported medication will be classified as ‘Prior’, ‘Prior and Concomitant’ or ‘Concomitant Only’:

- ‘Prior’: if the subject has not taken any IP; or if the medication end date is before IP start date. If the medication end date is partially missing, the medication will only be assigned to ‘Prior’ if the partial date gives clear evidence that the medication stopped before IP start;
- ‘Prior and Concomitant’: if the medication is not classified as ‘Prior’ or as ‘Concomitant Only’;
- ‘Concomitant Only’: if the medication started on or after IP start date. If the medication start or end date are partially missing, the medication will only be assigned to ‘Concomitant Only’ if the partial dates give clear evidence that the medication started on or after IP start.

Concomitant medications, i.e., medications classified as ‘Concomitant Only’ or ‘Prior and Concomitant’, will be summarized for the ITT Analysis Set by treatment and total showing the number and percentage of subjects taking concomitant medications by Anatomical Therapeutic Chemical (ATC) classification level 4 and preferred term. If the ATC level 4 coding is not available for a preferred term, the next available lower level ATC code will be used.

Concomitant medications flagged as anti-COVID-19-drugs will be summarized by treatment and total with their ATC classification showing the number and percentages of subjects stratified by prior use, prior and concomitant use, and concomitant only use. The duration of anti-COVID-19 drug use will be summarized descriptively for the categories prior, prior and concomitant, and concomitant only.

The following by-subject listings will be provided based on the ITT Analysis Set:

- Prior/concomitant medication;
- Use of anti-COVID-19 drugs.

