### 10.1.1 Primary Estimand

Clinical question of interest: Is there a treatment benefit of CSL312 after IV infusion in patients with COVID-19, i.e. does treatment with CSL312 + SOC reduce the risk to progress to tracheal intubation or to die prior to tracheal intubation in subjects with severe COVID-19 disease while subjects are treated with SOC?

The primary estimand in line with the primary interest of the study follows the treatment policy strategy and is described as follows:

- A. Subject population: the target subject population defined by eligibility criteria.
- B. Treatment condition of interest: One dose (700 mg) of IP (CSL312 + SOC or Placebo + SOC) via IV infusion on peripheral vein.
- C. Variable: subject’s progression to tracheal intubation or death prior to tracheal intubation at any time from randomization to Day 28.
- D. Intercurrent events:
  - 1. Concomitant use of anti-COVID-19 drugs.
  - 2. Early discontinuation of the study for any reason.
  - 3. Randomized without treatment.
- E. Population level summary: risk difference of progression to tracheal intubation or death prior to tracheal intubation (CSL312 + SOC minus placebo + SOC).

In this study, the treatment policy strategy will be used for all intercurrent events. It is reasonable to assume for subjects who are losses to follow-up after hospital discharge likely not to have experienced the event under randomized treatment. If subjects are still in hospital after withdrawal from the study (but not withdrawal of consent), missing data is unlikely to occur.

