#### **10.1.4 Subgroup Analyses for Progression to Tracheal Intubation or Death Prior to Tracheal Intubation**

Subgroup analyses by the variables defined in Sections 8.2.7.1, 8.2.7.2, 8.2.7.3, 8.2.7.4, and 8.2.7.5 will be performed using the ITT Analysis Set as described above in Section 10.1.2. The logistic regressions will not include the factor for the respective subgroup analysis as independent variable (if applicable), but they will include the other covariates as specified for the primary analysis.

A forest-plot will be provided for the estimated risk difference and 95% CIs for each subgroup level.

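### The anti-COVID-19 drug subgroup is set partly by drug starts after randomization, so its descriptive treatment contrasts can mislead (low priority)

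*SAP*

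**What the plan says.** SAP 8.2.7.4 splits subjects by "Any concomitant usage of anti-COVID-19 drugs during the trial: yes" against no such use. It sets no baseline cut-off and cites no derivation, whereas 8.2.7.3 points to 9.3 for comorbidity.

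SAP 9.4 sorts medications into three classes. A drug is *Concomitant Only* "if the medication started on or after IP start date". It is *Prior* "if the subject has not taken any IP; or if the medication end date is before IP start date". Everything else is *Prior and Concomitant*, which is where a baseline drug continuing past dosing falls. Concomitant means the first and third classes together. Section 9.4 also tabulates anti-COVID-19 drugs by arm across the three classes.

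SAP 10.1.1 lists "Concomitant use of anti-COVID-19 drugs" as the first intercurrent event and applies treatment policy to all of them. The subgroup analysis of the primary endpoint "will be performed using the ITT Analysis Set as described above in Section 10.1.2", with a forest plot. SAP 10.2.2 does the same for mortality, intubation and NIAID status. SAP 10.3 makes everything except the one confirmatory test descriptive.

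Two neighbouring rules are in SAP 10.1.3. The complete-case set is limited to Day 28 completers and deaths, although 10.1.3.1 does not treat a recorded intubation as missing. A further analysis, labelled sensitivity, counts an anti-COVID-19 drug start after randomization as a primary event.

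**The concern.** Sex, age, comorbidity and country are fixed before treatment. Anti-COVID-19 drug use during the trial is not: a drug may be started because the patient worsens, and worsening is what CSL312 is meant to prevent. If the arms differ in who starts, users on CSL312 and users on placebo are no longer comparable groups, and neither are the non-users. The forest plot could then show CSL312 working differently in the two groups when it does not.

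There is a second, conditional problem. If the 9.4 classes drive the split, every drug of a randomized but untreated subject is *Prior*. That subject is then a non-user whatever was given, in an analysis meant to be ITT.

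At stake is the reading of descriptive displays for four endpoints, not the trial's main claim.

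**Working it through.** **Planning figure.** With 30% vs 10%, two-sided alpha 0.05 and 80% power, n per arm = [1.96·√(2·0.2·0.8) + 0.8416·√(0.3·0.7 + 0.1·0.9)]² / 0.2² = (1.1087 + 0.4610)² / 0.04 = 61.6, so 62 per arm and 124 in all, as stated. Nothing below changes this.

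The documents give no rates of drug use, so all such rates below are assumptions. Differences are CSL312 minus placebo, in percentage points.

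**No true effect.** Assume 60% mild subjects (10% events) and 40% severe (60% events): 30% events in both arms. Placebo drug use is 30% in mild and 80% in severe subjects.

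- Placebo users: (0.6·0.3·0.1 + 0.4·0.8·0.6) / 0.50 = 0.21/0.50 = 42.0%.
- Placebo non-users: 0.09/0.50 = 18.0%.

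| Use on CSL312 | Users, CSL312 | Difference | Non-users, CSL312 | Difference |
|---|---|---|---|---|
| Same as placebo | 42.0% | 0 | 18.0% | 0 |
| Severe 70% | 0.186/0.46 = 40.4% | −1.6 | 0.114/0.54 = 21.1% | +3.1 |
| Severe 60% | 0.162/0.42 = 38.6% | −3.4 | 0.138/0.58 = 23.8% | +5.8 |
| Severe 50% | 0.138/0.38 = 36.3% | −5.7 | 0.162/0.62 = 26.1% | +8.1 |
| Mild 20% | 0.204/0.44 = 46.4% | +4.4 | 0.096/0.56 = 17.1% | −0.9 |
| Mild 10% | 0.198/0.38 = 52.1% | +10.1 | 0.102/0.62 = 16.5% | −1.5 |

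The sign depends on which patients change their drug use.

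**Both conditions are needed.** Let use be 50% in both strata on placebo and 30% in both on CSL312. Use differs by arm but is unrelated to risk. Users and non-users then have 30% events in each arm, and the bias is zero.

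**Uniform true effect of −20.** Assume 30% baseline use unrelated to outcome. Of the rest, 70% of progressors and 30% of non-progressors start a drug, by the same rule in both arms. The user share is 0.3 + 0.7·0.7 = 0.79 of progressors and 0.3 + 0.7·0.3 = 0.51 of non-progressors.

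- Users: placebo 0.237/0.594 = 39.9%, CSL312 0.079/0.538 = 14.7%; difference −25.
- Non-users: placebo 0.063/0.406 = 15.5%, CSL312 0.021/0.462 = 4.5%; difference −11.

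**Precision.** Half-width = 1.96·√[p₀(1−p₀)/n₀ + p₁(1−p₁)/n₁], unadjusted, with n = 62 × share. For severe use of 50%: users (31 vs 23.6) 26.1 points, non-users (31 vs 38.4) 19.4 points. Across the differing-use rows of the table: about 25 to 27 for users and 18 to 19 for non-users.

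**A harsher input.** Take no true effect, no baseline use, 70% of progressors starting, and starts among non-progressors cut from 40% to 20%. Users are 0.21/0.49 = 42.9% vs 0.21/0.35 = 60.0%, or +17.1. The half-width with 30.4 vs 21.7 users is about 27 points, so this too is within sampling error.

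**Complete-case set.** Start from 19/62 vs 6/62, a difference of −21.0. Dropping intubated subjects who leave alive gives:

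- 1 placebo, 0 CSL312: 18/61 vs 6/62 = −19.8
- 0 and 1: 19/62 vs 5/61 = −22.4
- 1 and 1: 18/61 vs 5/61 = −21.3
- 3 and 1: 16/59 vs 5/61 = −18.9

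**Drug start counted as an event.** The rate becomes 1 − (1−p)(1−s). With true rates of 30% vs 10% and equal start rates s of 10%, 30% or 50%, it is 37 vs 19, 51 vs 37 or 65 vs 55: differences of −18, −14 or −10. With no true effect, starts of 40% vs 25% give 58.0% vs 47.5%.

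**The case against.** The analyses are descriptive, and every bias above lies inside its subgroup's sampling error. The 9.4 table will show whether drug use differs by arm, so a careful reader is warned. Baseline users who continue their drug are in the user group anyway. The point about untreated subjects depends on using the 9.4 classes, which 8.2.7.4 does not say. The complete-case analysis is for reference only, consenting subjects stay to Day 28 (Protocol 6.4.1), and the SAP expects few missing outcomes. The drug-start analysis is openly defined, so only its name is at issue.

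Most of this stands and sets the priority. It does not rescue the definition. The 9.4 table can show that use differs but does not remove the bias, and its cut is dosing, not randomization. More subjects would shrink the sampling error but not the bias, and a baseline definition is available at almost no cost.

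Two stronger readings are tempting. A reader might infer that these contrasts are biased whenever treatment changes drug use. That fails: use must also be related to outcome risk, as the 50% vs 30% example shows. A reader might also infer that the primary result or type I error is at risk. The primary model in 10.1.2 does not use this variable, and 10.3 allows one confirmatory test, so the documents do not support that either.

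**Conclusion.** The point holds as a low-priority correction. Membership of the 8.2.7.4 subgroup is decided partly after randomization, by a variable that the SAP itself lists as an intercurrent event. Its contrasts for the primary endpoint, mortality, intubation and NIAID status can be biased if CSL312 changes drug use and use is related to risk. The main scenarios give about 1 to 10 points in either direction against half-widths of about 18 to 27; the harsher one gives 17 against 27. All rest on assumed rates of use, and the bias is zero if either condition fails. The risk is a misleading display, not a false confirmatory claim.

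The complete-case wording is a minor inconsistency with 10.1.3.1 that probably touches few subjects. The drug-start analysis is a matter of labelling: it targets a composite estimand, while 10.1.1 uses treatment policy throughout.

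**What to change.** In SAP 8.2.7.4, define users as ITT subjects, treated or not, with any anti-COVID-19 drug started before randomization. SAP 8.2.1 already supports that cut: "The reference date for efficacy is the date (and time) of randomization". Derive it from recorded medication dates, and times where available, rather than from the 9.4 classes. For partial start dates, require clear evidence of an earlier start, in the spirit of 9.4's own test for *Prior*: "the partial date gives clear evidence that the medication stopped before IP start".

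State one same-day rule for both arms. It matters because Protocol 9.1 lists start and end dates but no times, and because "Eligibility may be assessed at the time of hospital admission provided that the subject is randomized within 24 hours", so admission-day drugs may share the randomization date. The default should count an untimed same-day start as non-use: no start made after randomization can then put a subject in the user group, so this source of bias is removed. The cost is that some admission-day baseline users are classed as non-users. If 10%, 30% or 50% of an assumed 31 users per arm are affected, 31·(1−f) leaves about 28, 22 or 16. Run the opposite rule as a check. If 5% of severe placebo subjects start later that day, against 2.5% or 0% on CSL312, its residual bias is −0.4 or −0.75 points in users and +0.8 or +1.6 in non-users.

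In SAP 10.1.3, define complete cases as Day 28 completers plus anyone with an intubation or death on record. Relabel the analysis that counts a drug start as an event as supplementary (composite estimand), read beside the 9.4 counts by arm.

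The cost is SAP wording and minor reprogramming, with no new data. The user split may become less even, and some partial dates will be misclassified.

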#### **8.2.7.5 Subgroup: Country**

- USA;
- Brazil.

### **8.3 Study Periods Relative to Treatment**

**Screening Period** starts with the date (and time) of the signed informed consent and ends before the date (and time) of randomization.

**Treatment Period** starts with the date (and time) of randomization and ends on the Day 28 visit.

**EOS** is at Day 28, the last day of the Treatment Period.

## **9 Study Population**

Unless otherwise stated, tables in this section will be based on the ITT Analysis Set. Listings will be based on the ITT Analysis unless otherwise stated.

### **9.1 Subject Disposition**

Number and percentage of subjects will be presented in a summary table for the Screened Analysis Set (where meaningful by treatment and total) including the following information:

- Subjects who underwent Screening – only total;
- Screening failures with reason for failure – only total;
- Subjects randomized – by treatment and total;
- Subjects randomized but not treated – by treatment and total;
- Subjects treated – by treatment and total;
- Subjects treated who completed the study – by treatment and total;
- Subjects treated who discontinued from the study with reason – by treatment and total.

Reasons for study discontinuation will be presented in the order they are displayed in the CRF.

Number and percentage of randomized subjects per site and country will be presented.

The following by-subject listings will be provided including all available data:

- Randomization scheme based on the ITT Analysis Set;
- Subject disposition with date of Screening (in case of re-screening, all screening records will be listed), date (and time) of the randomization, date (and time) of IP administration, Day 28 date/date of withdrawal;
- Screening failures with reason;
- Subjects who discontinued from the study with reason for discontinuation.

## 9.2 Protocol Deviations / Reasons for Exclusion From Analysis Sets

A protocol deviation occurs when an investigator, site, or study subject, does not adhere to protocol-stipulated requirements. Deviations will be assessed by CSL as they are reported and then evaluated periodically during study conduct.

In this study, protocol deviations will not lead to exclusion of a subject from an analysis set.

Other reasons than protocol deviations may exist to exclude a subject from an analysis set. The final decision about the assignment of subjects to analysis sets will be made during the Blind Data Review Meeting prior to database lock.

The list of reasons presented in Table 2 may lead to exclusion of a subject from an analysis set and will be discussed during the Blind Data Review Meeting. The list may be modified, and other reasons may be added. The final decision about the exclusion of subjects from analysis sets will be made during the meeting and will be documented in the meeting minutes.

